2.16 Pooling Strategy for Strata

The number of subjects randomized is quite large relative to the number of strata. As such, no pooling of strata is planned for data analysis.

2.17 Safety Analyses

Statistical analyses will be descriptive in nature and will not be routinely tested for statistical significance. Safety analyses will be based upon the clinical database only. Events recorded in the safety database will be reconciled with the clinical database prior to database lock.

The primary safety analyses will be conducted using all data. Some sensitivity analyses using the data cutoff as June 24, 2021 may be undertaken, as appropriate.

For subjects who were in the Run-in Phase twice, data from the second Run-in will be summarized. Data from the first Run-in will be included in listings only.

2.17.1 Adverse Events

Adverse events (AEs) and serious adverse events (SAEs) coded using MedDRA (MedDRA version 23.0 or an updated version), including all-cause mortality, will be summarized descriptively.

AE summaries will be provided separately for the Run-in Phase and the Blinded Treatment Phase in the SS.

AE summaries will consist of counts (%) by MedDRA SOC and PT in the Run-in Phase, and by MedDRA SOC, PT and treatment arm in the Treatment Phase. The following types of AEs will be summarized:

- All treatment emergent adverse events (TEAEs)
- TEAEs by severity
- TEAEs related to study medication (patiromer/placebo)
- TEAEs leading to study medication discontinuation (patiromer/placebo)
- SAEs
- SAEs related to study medication (patiromer/placebo)

AE summaries will also be presented in the Run-in Phase Set.

A listing of AEs will be provided, to include verbatim term, preferred term (PT), system organ class (SOC), intensity/severity, relationship to patiromer/placebo, whether serious, onset/end date, action taken and outcome of event.

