6.7.3 Temporary Interruption or Dose Reduction of HF Medications

During the Treatment Phase, temporary interruption or dose reduction of HF medications is allowed, with documentation of the reason for the change. HF medications may be reinitiated at the time that is deemed appropriate by the Investigator, and HF medications may be titrated as needed.

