10.4.2 Causality and Reporting

The Investigator will provide a causality assessment for all AEs using his/her best clinical judgment based upon the available medical information of the event that is being reported. The causality assessment will be re-assessed as new medical information becomes available. If the Investigator's causality assessment is not reported it will be considered as "related" until it is received. The Investigator will each assess relatedness of the AE to the investigational drugs, patiromer/placebo, using the following definitions:

Not Related: There is no reasonable possibility that patiromer caused or contributed to the AE.

- The event is related to an etiology other than the investigational drug such as underlying disease, study or non-study procedures, concomitant medications, or the subject's clinical state
- The time of the occurrence of the AE is not reasonably related to the administration of the study drug

Related: There is a reasonable possibility that patiromer caused or contributed to the AE.

- There is a compatible temporal association between the event and the administration of investigational drug
- There is a biologically plausible mechanism for the study treatment to cause or contribute to the AE
- The event improves or diminishes upon withdrawal of the study drug without the initiation of any specific treatments for the event (dechallenge), and/or the event recurs or worsens with the rechallenge of the study therapy
- The event cannot be reasonably attributed to concurrent or underlying illness, other drugs, or procedures

For causality assessment purposes “reasonable possibility” is meant to convey that, based on the Investigator’s medical judgment of the available information, there are facts or arguments to suggest a positive causal relationship.

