12.9 Safety Evaluations

The following safety variables will be summarized using the safety set:

- AEs and SAEs (coded using Medical Dictionary for Regulatory Activities (MedDRA); see Study Manual for MedDRA version), including all-cause mortality
- Slope of eGFR change during the study will be estimated and compared between treatment groups using a repeated measures analysis with time treated as a continuous variable
- Decline in eGFR >50% or ESRD, renal death, or need for dialysis
- Laboratory parameters other than those defined as efficacy endpoints

AE summaries will be provided separately for: (1) AEs with start date on or after first dose date during the Run-in Phase and on or before the date of randomization; and (2) AEs with start date on the day after randomization. Summaries will consist of counts (%) by system organ class (SOC), preferred term (PT) and severity in the Run-in Phase, and by SOC, PT, severity, and treatment in the blinded withdrawal phase. The following types of AEs will be summarized:

- All treatment-emergent adverse events (TEAEs)
- TEAEs related to study medication (patiromer/placebo) and to RAASI
- TEAEs leading to study medication discontinuation (patiromer/placebo) and to RAASI discontinuation
- SAEs

A listing of AEs will be provided, to include verbatim term, PT, SOC, intensity/severity, relationship to patiromer/placebo, and to RAASI, whether serious, onset/end date, action taken and outcome of event.

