3 CHANGES FROM THE PROTOCOL

The protocol specifies that blood samples be taken during the study in order to analyse subject MRA levels.

The complete, validated MRA concentration data will not be available at the time of database lock, and analyses of that data will not be included for the CSR. The complete and validated data will be delivered later and analysed separately.

Slope of eGFR change during the study was proposed as a safety endpoint in the protocol. In the SAP it has been changed to an efficacy endpoint, and will be analysed using an mrrm model similar to those used for other efficacy endpoints.

Analyses during Run-in have been added to the SAP.

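### SAP 2.17.1 drops, without declaring it, the three RAASi-specific adverse event outputs in protocol 12.9, and the protocol is itself inconsistent on RAASi causality

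*SAP*

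**What the plan says.** Protocol 12.9 lists four types of adverse event summary, and two of them name RAASi as well as study drug: "TEAEs related to study medication (patiromer/placebo) and to RAASI" and "TEAEs leading to study medication discontinuation (patiromer/placebo) and to RAASI discontinuation". It also specifies a listing that shows "relationship to patiromer/placebo, and to RAASI, whether serious, onset/end date, action taken and outcome of event".

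SAP 2.17.1 has the corresponding items without RAASi: "TEAEs related to study medication (patiromer/placebo" and "TEAEs leading to study medication discontinuation (patiromer/placebo", each ending at the closing bracket. Its listing gives relationship to patiromer/placebo only.

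SAP Section 3 declares three changes: MRA concentration data will be analysed later, eGFR slope moves from safety to efficacy, and "Analyses during Run-in have been added to the SAP". Nothing there concerns RAASi and adverse events.

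On what is recorded, protocol 10.4.2 states: "The Investigator will each assess relatedness of the AE to the investigational drugs, patiromer/placebo, using the following definitions". The SAE minimum data in 10.7.2 ask for relationship to, and action taken with, patiromer/placebo. Protocol 6.7.3 says that in the Treatment Phase "temporary interruption or dose reduction of HF medications is allowed, with documentation of the reason for the change".

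**The concern.** The protocol's rationale (Section 2) is that patiromer controls potassium so that subjects can stay on guideline RAASi treatment. Key secondary endpoint 2 credits staying on the 50 mg MRA target dose. The protocol itself names harms that limit RAASi: renal function decline and symptomatic hypotension in 6.7.2, and eGFR declines that call for RAASi reduction or discontinuation in 6.7.4. If patiromer does keep more subjects on full doses, such events are a plausible cost of the benefit. The RAASi-specific outputs in 12.9 are where that cost would be visible as attributed events and as AE-driven stops.

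The silence also matters. Protocol 12.1 requires deviations from the SAP to be explained in the final report. An output removed inside the SAP, and not listed in SAP Section 3, is not a deviation from the SAP, so nothing obliges the report to mention that it is gone.

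**Working it through.** There is no figure to recompute; the check is a comparison of texts. None of the sections compared in step 1 is redacted.

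**Step 1: planned against kept.**

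| Output | Protocol 12.9 | SAP 2.17.1 | Declared in SAP Section 3 |
|---|---|---|---|
| Relatedness summary | Study drug and RAASi | Study drug only | No |
| Discontinuation summary | Study drug and RAASi | Study drug only | No |
| AE listing, relationship | Study drug and RAASi | Study drug only | No |

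That is 3 RAASi-specific outputs planned, 0 kept and 0 of 3 removals declared. Two of the four summary types in 12.9 are affected, plus one listing item.

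**Step 2: can the data support them?** For relatedness, 10.4.2 and 10.7.2 define an assessment for patiromer/placebo only. Under 10.4.2 an event attributed to concomitant medication is classed as not related, so an event put down to RAASi also falls outside the one relatedness summary that the SAP keeps. Yet the 12.9 listing presupposes that a RAASi item exists. These sections disagree, and the eCRF that would settle it is not in the documents.

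For discontinuation, 6.7.3 requires a documented reason for a temporary interruption or dose reduction in the Treatment Phase. It does not name permanent discontinuation, and it does not say that the reason is held in the eCRF or tied to an AE record. Protocol 10.5.4 helps in part: a laboratory result that leads to a change in concomitant therapy must be reported as an AE. The summary is therefore plausible to produce, but not assured.

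**Step 3: does another planned output replace what was dropped?**

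- All TEAEs, TEAEs by severity and SAEs (SAP 2.17.1) show events by arm, but not whether they led to a RAASi change.
- Time to MRA discontinuation and time to ACEi/ARB/ARNi discontinuation (SAP 2.9, 2.10.3) are defined in 2.9 without regard to reason, count only stops with no re-introduction, and use data through June 24, 2021. Analysis details in 2.10.3 are blacked out, so this rests on the definitions in 2.9.
- Percentages of subjects at 50% and 100% of target dose by visit (SAP 2.8) carry no reasons.
- The renal composite (SAP 2.17.2) starts at an eGFR decline above 50%. The 31–50% band, which protocol 6.7.4 links to a RAASi dose decrease, lies below it.
- By-visit laboratory summaries (SAP 2.17.2) use central values, whereas the Schedule of Events has creatinine measured only locally at Day 3 and Weeks 1, 2 and 6. Local results are promised in listings.

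Each reports part of the picture. None joins an adverse event to a RAASi stop.

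**The case against.** The strongest reply is that nothing of substance is hidden. The trial is randomized and double-blind, so if patiromer leads to more RAASi harm, the by-arm tables of preferred terms will show it without any investigator attribution. Hypotension appears as a preferred term, and vital signs are summarized by visit. An eGFR decline above 50% must be reported as an AE under protocol 6.7.4, and both the renal composite and the eGFR slope are reported. RAASi stopping is itself an endpoint. All the dropped items are descriptive, and if RAASi relatedness was never recorded, dropping it costs nothing.

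Much of this stands. A reader might infer from the omission that RAASi harm goes unreported. The documents do not support that: the harms are reported by arm, and only attribution and the link to RAASi stops are missing. A reader might also infer from 10.4.2 that RAASi relatedness is never collected. That is not shown either, because 12.9 calls for the item and the eCRF cannot be seen. Nor does 6.7.3 prove that the discontinuation table can be built, for the reasons in step 2.

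The reply does not meet two points. The removal of protocol-specified safety outputs is undeclared whatever their value. And no planned summary says how many RAASi stops in each arm were driven by adverse events, as opposed to potassium management or other reasons. At best a reader could try to match AE and medication listings by subject and date.

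**Conclusion.** The point holds as an undeclared omission together with an inconsistency inside the protocol. All three RAASi-specific adverse event outputs of protocol 12.9 are absent from SAP 2.17.1, and SAP Section 3 declares none of the removals. The loss of consequence is the by-arm summary of TEAEs leading to RAASi discontinuation, which would let the trial say whether RAASi stops were driven by adverse events. The relatedness items need only be reconciled or declared.

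The documents give no figure for how many events or stops are involved, so the clinical size of the loss cannot be stated. No alpha, power or tested endpoint is touched. The change should be made, but the trial's main inference does not depend on it. The conclusion assumes that no redacted text in SAP 2.10.3 breaks the discontinuation endpoints down by reason. The feasibility of the fix depends on the eCRF.

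**What to change.** 1. In SAP 2.17.1, restore the summary of TEAEs leading to RAASi discontinuation, by arm in the Safety Set and by SOC and PT. Build it from the AE record and the documented reason for change (protocol 6.7.3), after confirming that the eCRF supports it. Splitting MRA from ACEi/ARB/ARNi and adding dose reductions would be useful, but goes beyond what protocol 12.9 asks.
2. If the eCRF captured RAASi relatedness, restore the summary and the listing column. If it did not, say so in SAP Section 3, justify the removal, and reconcile protocol 12.9 with 10.4.2 and 10.7.2. Starting to collect it now is not practical: SAP 2.2 describes site conduct after the closure notice of June 24, 2021 in the past tense, so any collection would be retrospective.
3. If the discontinuation data also prove inadequate, declare that in SAP Section 3 in the same way.

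The cost is one extra descriptive table, some programming to link the reason for change to the AE, and a short addition to SAP Section 3.

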5.5 Discontinuing Patiromer/Placebo or Withdrawal of Subjects

5.5.1 Discontinuation from Patiromer/Placebo

The management of ACEi/ARB/ARNi and/or MRA are at the discretion of the Investigator during the Blinded Treatment Phase. If one or more ACEi/ARB/ARNi and/or MRA are adjusted, patiromer/placebo may be adjusted accordingly, based on changes in local serum K^+ levels. The lowest dose of patiromer/placebo is 0 packets/day. It is recommended to discuss with the subject a study treatment interruption (dose level 0 packets/day) rather than a permanent patiromer/placebo discontinuation, which should only occur when it is requested by the Investigator or the subject.

Subjects who discontinue from patiromer/placebo treatment after randomization and prior to completion of the study will be encouraged to return within 2 weeks, or as soon as possible thereafter, for a Potassium Assessment Visit (see Section 8.6). Subjects who

discontinue from patiromer/placebo treatment after randomization and prior to the common EoS will continue in the study for collection of composite endpoint events. These subjects will be treated in accordance with the standard of care per the Investigator's judgment.

Note: Subjects who discontinue from patiromer during the Run-in Phase will also be encouraged to return for a Potassium Assessment Visit within 2 weeks, or as soon as possible thereafter.

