6.3.2 Dosing and Administration Guidelines

6.3.2.1 Patiromer/Placebo

The starting dose will be 1 packet/day and may be taken either with food or without food. Based upon the K⁺ management algorithms (Section 6.7.1.1 and Section 6.7.1.2),

patiromer/placebo may be increased by 1 packet per day in intervals of at least 1 week (± 3 days). For subjects who become hypokalemic ($K^+ < 4.0$ mEq/L), patiromer/placebo must be decreased to a minimum of 0 packets/day (see Section 6.7.1.1). If serum K^+ increases from $< 4.0 - \geq 4.0$ mEq/L and remains between $\geq 4.0 - \leq 5.0$ mEq/L, patiromer/placebo must not be resumed yet. Resume patiromer/placebo only when $K^+ > 5.0$ mEq/L to prevent re-inducing or aggravating hypokalemia. Doses of patiromer/placebo will be 0 packets/day, 1 packet/day, 2 packets/day, and 3 packets/day (maximum dose).

Patiromer/placebo are for oral administration only. Each dose must be prepared immediately prior to administration. Patiromer/placebo should be taken at least 3 hours before or 3 hours after administration of other orally administered medications. Patiromer/placebo should be taken once daily, and preferably at the same time of day, consistently. An accidentally missed dose can be taken later on the same day but shall not be taken the next day. At the discretion of the Investigator, the following drugs may be co-administered with patiromer/placebo: allopurinol, amlodipine, amoxicillin, apixaban, aspirin, atorvastatin, cephalexin, cinacalcet, clopidogrel, digoxin, furosemide, glipizide, lisinopril, lithium, metoprolol, phenytoin, rivaroxaban, spironolactone, trimethoprim, valsartan, verapamil, and warfarin (see the Investigator's Brochure (IB), Version 13.0, dated 15 July 2020, for additional information [30]).

Patiromer/placebo suspension must not be heated (e.g., microwaved) or added to heated foods or liquids. Patiromer/placebo must not be taken in its dry form but must be mixed with water, apple, or cranberry juice only. Prepare patiromer/placebo doses following the steps below:

- Measure 1/3 cup (approximately 80 mL) of water. Pour half of the water into a glass, then add the contents of the prescribed number of patiromer/placebo packets and stir. Add the remaining half of the water and stir thoroughly. The powder will not dissolve, and the mixture will look cloudy. Add more water to the mixture as needed for desired consistency

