- If local serum K⁺ is ≥4.3-≤5.0 mEq/L at the first week during the Run-in Phase, patiromer must be started at 1 packet/day
- If local serum K⁺ is ≥4.0-≤4.3 mEq/L at the first week during the Run-in Phase, patiromer may be started at 1 packet/day; initiation or increase of patiromer dose should be made with caution when local serum K⁺ is ≥4.0-≤4.3 mEq/L to avoid inducing hypokalemia

- If local serum K^+ decreases from >4.3 mEq/L to values <4.3 mEq/L, remaining ≥ 4.0 mEq/L, patiromer may be down-titrated by 1 packet/day (minimum dose is 0 packets/day); in case of a reversal of this decrease from <4.3 mEq/L but remaining ≥ 4.0 mEq/L to values ≥ 4.3 mEq/L at following visits, patiromer may be up-titrated by 1 packet/day; subjects must receive at least 1 packet/day at serum $K^+ \geq 4.3 - \leq 5.0$ mEq/L
 - If 1 week after reducing patiromer to 0 packets/day local serum K^+ remains stable $\geq 4.0 - \leq 4.3$ mEq/L, optimize RAASi dose and resume patiromer at 1 packet/day before considering these subjects as Run-in failed; initiation or increase of patiromer dose should be made with caution when local serum K^+ is $\geq 4.0 - \leq 4.3$ mEq/L to avoid inducing hypokalemia
- If local serum K^+ is <4.0 mEq/L, patiromer must be down-titrated to 0 g/day (i.e., 0 packets/day), with confirmation of hypokalemia within 3 days and follow-up in at least (\geq) 1-week intervals until serum K^+ is ≥ 4.0 mEq/L. Resume patiromer only when local serum K^+ rises to >5.0 mEq/L
 - If 2 weeks after taking the minimum 0 packets/day, local serum K^+ remains <4.0 mEq/L during the Run-in Phase, then subject is Run-in failed

Once a subject meets all randomization criteria (see Section 5.4), they may be randomized into the Treatment Phase (double-blinded).

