The Investigator reinitiates patiromer/placebo treatment after a temporary interruption of dosing per treatment algorithm described in Section 6.7.1.1.

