10.5.4 Clinical Laboratory Evaluations

Not every out-of-range laboratory result qualifies as an AE. A laboratory investigation result must be reported as an AE if it meets any of the following criteria:

- Is accompanied by clinical symptoms
- Results in a change in study treatment (e.g., dosage modification, treatment interruption, or treatment discontinuation). For the purpose of this study, AEs should be reported if $K^+ < 4.0 \text{ mEq/L}$ or $> 5.0 \text{ mEq/L}$
- Results in a medical intervention (e.g., K^+ supplementation for hypokalemia) or a change in concomitant therapy

- Presents shift of a parameter from a normal value to a pathological value or a further worsening of an already pathological value
- Is clinically significant in the Investigator's judgment

It is the Investigator's responsibility to review all laboratory findings. Medical and scientific judgment should be exercised in deciding whether an isolated laboratory abnormality should be classified as an AE. When evaluating such changes, the extent of deviation from the reference range, the duration until return to the reference range, either while continuing treatment or after the end of treatment with the investigational product, and the range of variation of the respective parameter within its reference range, must be taken into consideration.

The Investigator has the responsibility to determine the clinical significance of each abnormality.

If, at the end of the Treatment Phase, there are pathological laboratory values which were not present at Baseline, further clinical or laboratory investigations should be performed until the values return to within reference range or until a plausible explanation (e.g., concomitant disease) is found for the pathological laboratory values.

The Investigator should decide, based on the above criteria and the clinical condition of a subject, whether a change in a laboratory parameter is clinically significant and therefore represents an AE. If the Investigator considers such an AE as serious (e.g., medically significant event fulfilling criteria per Section 10.7.1), it must be reported as an SAE.

If a laboratory abnormality meeting the above criteria is a sign of a disease or syndrome only the diagnosis should be recorded in the eCRF.

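### SAP 2.17.1 tabulates only TEAEs leading to discontinuation, although the protocol prefers interruption at 0 packets/day, so AE-driven stops handled that way are not counted by arm

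*SAP*

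**What the plan says.** Protocol 5.5.1 recommends discussing with the subject a "study treatment interruption (dose level 0 packets/day) rather than a permanent patiromer/placebo discontinuation", and says of the permanent kind: "which should only occur when it is requested by the Investigator or the subject". Protocol 6.3.2.1 lists zero as an ordinary dose: "Doses of patiromer/placebo will be 0 packets/day, 1 packet/day, 2 packets/day, and 3 packets/day (maximum dose".

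The protocol treats interruption and discontinuation as different actions. Section 10.5.4 names them separately among the study drug changes that make a laboratory result reportable: "Results in a change in study treatment (e.g., dosage modification, treatment interruption, or treatment discontinuation". Section 6.7.1.2 expects interrupted subjects to restart: "The Investigator reinitiates patiromer/placebo treatment after a temporary interruption of dosing".

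SAP 2.17.1 plans six types of AE summary: all TEAEs, by severity, related, leading to discontinuation, SAEs, and related SAEs. Only one depends on the action taken: "TEAEs leading to study medication discontinuation (patiromer/placebo". Action taken otherwise appears only in the AE listing. Protocol 12.9 has action-based summaries for study drug discontinuation and RAASi discontinuation, and none for interruption or dose reduction.

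**The concern.** The share of subjects who stop drug because of an adverse event is a tolerability figure that readers look for first. Here the protocol directs stops towards a category that the planned table does not count. A subject who goes to 0 packets/day because of a gastrointestinal event, or because of low potassium, is off drug because of an AE but need not be a discontinuation. If this happens at all, the tabulated rate is too low. If it happens to a different extent in the two arms, the comparison is distorted as well.

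**Working it through.** **No figure to reproduce.** Neither document states an expected rate of AE-driven stopping, so the check is a comparison of texts followed by simple algebra.

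**Step 1: can an AE take a subject off drug without a discontinuation?** Yes. Protocol 5.5.1 prefers interruption, 6.3.2.1 makes zero a dose level, and 10.5.4 and 6.7.1.2 keep interruption apart from discontinuation. Low potassium is a concrete route. Section 10.5.4 asks for AEs to be reported when K+ is below 4.0 mEq/L. Section 6.3.2.1 provides for blinded drug to be decreased, down to 0 packets/day, in hypokalemic subjects, with resumption only above 5.0 mEq/L. A subject whose potassium settles between these values could stay at zero for some time without being discontinued. (The Run-in rule in 6.7.1.1, "patiromer must be down-titrated to 0 g/day (i.e., 0 packets/day", is single-arm and says nothing about a between-arm difference.)

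**Step 2: does another planned output give AE-linked counts by arm?** No.
- The AE listing carries action taken but gives no counts.
- Titration counts and non-zero dose days (SAP 2.7) are by arm but are not tied to AEs, so they mix AE-driven with potassium-driven changes.
- Compliance (SAP 2.7) is dose taken divided by dose prescribed. A day prescribed at zero adds nothing to either term.
- Duration (SAP 2.7) is last dose date minus first dose date plus 1, so interrupted days before a restart count as exposure.
- The primary exposure analyses use all data, including the time after 24 June 2021, when SAP 2.2 says many sites wrongly titrated or stopped blinded drug. An exposure analysis limited to that date is only optional.

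**Step 3: effect on the table.** Let p be the true proportion of an arm that stops drug because of an AE, and s the share of those stops handled only by interruption or 0 packets/day. The table shows p × (1 − s). With equal s in both arms, the difference shown is (p₁ − p₂) × (1 − s), and the ratio p₁/p₂ is unchanged.

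The following illustrates the mechanism with assumed p of 6% for patiromer and 3% for placebo, and the planned 410 per arm (SAP 1.5). It is not an estimate.

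| s, both arms | Patiromer shown | Placebo shown | Difference shown |
|---|---|---|---|
| 0% | 6.0% (about 25) | 3.0% (about 12) | 3.0 points |
| 25% | 4.5% (about 18) | 2.25% (about 9) | 2.25 points |
| 50% | 3.0% (about 12) | 1.5% (about 6) | 1.5 points |
| 75% | 1.5% (about 6) | 0.75% (about 3) | 0.75 points |

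If s differs by arm, the ratio moves too. With s = 50% for patiromer and 0% for placebo, the table shows 6% × 0.5 = 3% against 3%, and the difference disappears. With s = 25% and 75%, it shows 6% × 0.75 = 4.5% against 3% × 0.25 = 0.75%. That difference is 3.75 points, larger than the assumed true 3.0.

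**The case against.** The strongest reply is that little is concealed. SAP 2.17.1 tabulates all TEAEs by SOC, preferred term and arm, so an imbalance in constipation, diarrhea or hypokalemia would be seen. SAP 2.17.2 summarises serum potassium below 3.0, 3.5 and 3.8 mEq/L by arm, and SAP 2.7 gives time off drug through non-zero dose days. This stands, and it rules out the inference that the plan hides any difference between arms. What is missing is narrower: how often those events took subjects off drug.

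A reader might also infer that the protocol steers intolerant subjects away from discontinuation, and that most AE-driven stops will be recorded as zero packets. The text does not support either. The recommendation in 5.5.1 follows sentences on RAASi adjustment and potassium, does not mention intolerance, and leaves permanent discontinuation open on request. It covers anyone for whom stopping is discussed. That includes AE-driven cases, but no frequency follows.

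A third objection is that going to 0 packets/day for low potassium is the dosing algorithm at work, so one combined count could be dominated by algorithm-driven holds and would not measure tolerability. This is right, and it shapes the fix.

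Finally, the true rates may be small. Protocol 7.2 reports constipation in 5.9% and diarrhea in 4.9%, generally mild to moderate, and randomized subjects have already passed a patiromer run-in at a dose of at least 1 packet/day. This is fair, and it is a reason not to attach a headline percentage to the point.

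**Conclusion.** The concern holds as a tabulation gap that should be closed. Followed as written, the only action-based AE table omits AE-driven stops handled by interruption or 0 packets/day. The direction is established: such stops are not counted, so the table understates AE-driven stopping unless there are none. The effect on the comparison may be attenuation, if the omitted share is similar in both arms, or distortion, if it differs. Because patiromer lowers potassium, a larger omitted share in that arm is plausible, but that is an inference and neither document states it.

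The size cannot be derived from the documents. The conclusion assumes that SAP 2.17.1 uses discontinuation as the protocol does, apart from interruption. The SAP does not define the term. If it was meant to include interruptions, the undercount would fall away, but the definition would still be needed. No endpoint, test, alpha or sample size is affected, and the safety analyses are descriptive.

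**What to change.** In SAP 2.17.1:
- State that discontinuation means permanent discontinuation of study drug.
- Add TEAEs leading to dose reduction or interruption, including to 0 packets/day, by SOC and preferred term, for each phase, and by arm in the Treatment Phase.
- Add TEAEs leading to interruption or discontinuation combined, in the same layout. Count a move to 0 packets/day as an interruption even if the site recorded it as a reduction.
- Show each addition separately for low-potassium events, which capture the algorithm-driven holds, and for all other events.

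Optionally, add to SAP 2.7 the percentage of subjects by arm whose last prescribed dose on or before 24 June 2021 was 0 packets/day. Label it as descriptive exposure and not as a tolerability measure.

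The sources are the AE action-taken field and the dosing records, both already collected. The case report form is not among the documents. If its action-taken field does not separate interruption from reduction, dosing dates would have to be matched to AE dates. No dosing rule changes. The cost is a little more tabulation and a tolerability figure that may look less favourable.
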